## 1. OVERVIEW

### **Title**

A Phase 2 Study of Aminolevulinic Acid (ALA) to Enhance Visualization and Resection of Tumors of the Brain

### **Primary Objective**

To determine if the use of 5-aminolevulinic acid (ALA) helps distinguish tumor cells from normal cells leading to an increase in the amount of tumor removal during neurosurgical resection of glioma.

### **Secondary Objective**

Determine the safety of a single dose of 5-aminolevulinic acid (ALA) administered preoperatively at a dose of 20 mg/kg body weight.

### **Study product and route of administration**

5-Aminolevulinic Acid (ALA) will be given orally at a dose of 20 mg/kg body weight.

### **Participants**

300 individuals (age 18 to 72 years) with diagnosed glioma (WHO GI-IV) eligible for surgery will be entered into the trial.

50 participants will be enrolled into each of the following subgroups:

- 1) Newly diagnosed GBM
- 2) Newly diagnosed grade II glioma (astrocytic, oligodendroglial, and mixed)
- 3) Recurrent GBM
- 4) Recurrent grade III glioma (astrocytic, oligodendroglial, and mixed)
- 5) Newly diagnosed low grade glioma (astrocytic, oligodendroglial, ganglioglial, and mixed)
- 6) Recurrent low grade glioma (astrocytic, oligodendroglial, ganglioglial, and mixed)

### **Design**

Single center open label phase 2 trial

### **Estimated total study duration**

Twenty four months

### **Investigational New Drug (IND) sponsor**

[name]., Director, Brain Tumor Research Center  
University of California Medical Center, San Francisco

**Study drug provider**

DUSA Pharmaceuticals/Sun Pharma, Tarrytown, NY

**Statistical and data management**

UCSF Department of Neurological Surgery

**Safety Monitoring**

Adverse events will be collected from the time of drug administration. NCI Common Terminology Criteria for adverse events (CTCAE) version 3.0 will be utilized for adverse event reporting.

**2. OBJECTIVES****2.1 Primary Objective:**

To determine if the use of 5-aminolevulinic acid (ALA) helps distinguish tumor cells from normal cells leading to an increase in the amount of tumor removal during neurosurgical resection of glioma.

**2.2 Secondary Objective:**

Determine the safety of a single dose of 5-aminolevulinic acid (ALA) administered preoperatively at a dose of 20 mg/kg body weight.

**3. BACKGROUND**

[figure not shown]
Gliomas are locally invasive tumors in the brain that are very infiltrative and are associated with a poor prognosis. Currently there is no adequate way to properly identify these tumors during the course of surgical resection other than by gross visualization. A number of studies have shown that the extent of resection definitely affects outcome in terms of survival and progression-free survival (1-6). Nevertheless, surgical studies (2-7) have indicated that complete resection of contrast-enhancing tumor is achieved in only about 20-30% of patients and can be considered likely due to difficulty in determining the overall marginal area of the tumor (2). Therefore, it is considered important to achieve the greatest extent of resection possible, reducing the mass of the tumor, prior to administered therapy. Several technical surgery supports have been explored that include magnetic resonance imaging (MRI) (8), neuronavigation (9), and ultrasound (10) but little data from prospective randomized trials exists. The standard mode being used, with few exceptions, still relies on preoperative imaging studies to guide the course of resection, as well as the use of clinical acumen.

Over the last several years, 5-aminolevulinic acid (ALA) has been used in Europe to illuminate the tumor and its infiltrative margin and to compare it to white light-based surgery (11) and has been granted marketing approval by the European Medicines Evaluation Agency for use in the European community in adult patients for visualization of malignant tissue during

surgery for malignant glioma (World Health Organization Grades III and IV). ALA is a natural biochemical precursor of hemoglobin that elicits synthesis and accumulation of fluorescent porphyrins in various epithelia and cancerous tissue (12). ALA has been shown in experimental and clinical studies to be taken up by malignant glioma cells, where it is converted into fluorescing porphyrins (13). Strummer, et al. 2006, reports that fluorescence-guided resection by use of 5-aminolevulinic acid (ALA) is easy to do, and does not interrupt the operation (11). Such resection relies on specific synthesis and accumulation by 5-aminolevulinic acid of fluorescent porphyrins in malignant glioma tissue (14, 15). The technique differs from earlier attempts to use a fluorescent agent, such as fluorescein (16), in which the fluorescing agent is in the plasma and reaches the tumor through the disrupted blood-brain barrier, limiting specificity. The European data has been very supportive in terms of facilitating the extent of resection and improving 6-month progression-free survival (11).

### 3.1 5-Aminolevulinic Acid (ALA)

C5H9NO3 MW 167.6

ALA is a naturally occurring substance that is found in all organisms, including humans, and is necessary for part of the basic metabolic life processes. Approximately 350 mg of ALA is synthesized in humans each day for endogenous heme production. Administration of exogenous 5-ALA results in the production of high intracellular (mitochondrial) concentrations of Protoporphyrin IX (Pp IX). ALA (and other porphyrins) and Pp IX are excreted in the urine and the stool (via bile), respectively. DUSA Pharmaceuticals/Sun Pharma is located in Tarrytown, NY and will be the provider of the product. DUSA Pharmaceuticals/Sun Pharma has investigated the use of ALA and studied its pharmacology, pharmacokinetics, and toxicity.

#### *Pharmacology*

The metabolism of aminolevulinic acid is the first step in the biochemical pathway resulting in heme synthesis. ALA is not a photosensitizer, but rather a metabolic precursor of Pp IX, which is the photosensitizer. Synthesis of ALA is normally controlled by feedback inhibition of the enzyme, ALA synthetase, presumably by intracellular heme levels. ALA, when provided to the cell, bypasses this control point and results in the accumulation of Pp IX, which is converted into heme by ferrochelatase through the addition of iron to the Pp IX nucleus.

#### *Pharmacokinetics*

ALA and Pp IX were measured in plasma in a human pharmacokinetic study using a 128 mg dose of sterile intravenous ALA HCl and oral ALA HCl (equivalent to 100 mg ALA). The mean half-life of ALA was  $0.70 \pm 0.18$  hour after the oral dose and  $0.83 \pm 0.05$  hour after the intravenous dose. The oral bioavailability of ALA was 50-60% with a mean Cmax of  $4.65 \pm 0.94$  µg/mL. Pp IX concentrations were low and were detectable only in 42% of the plasma samples. Pp IX concentrations in plasma were quite low relative to ALA plasma concentrations, and were below the level of detection (10 ng/mL) after 10 to 12 hours.

#### *Toxicity*

Confidential

*In vivo* pharmacological and toxicological effects that may be associated with elevated systemic levels of ALA, Pp IX, and other intermediates of porphyrin biosynthesis in humans are well known, and characterize a group of metabolic diseases known as the porphyrias. An association between high systemic concentrations of ALA and neurological abnormalities is observed in Acute Intermittent Porphyria (AIP). However, attempts at clarifying the association between elevated ALA and the neurological symptoms of AIP have led to inconsistent results and contradictory conclusions. Most studies have shown that ALA and Porphobilinogen (PBG equals condensation of 2 molecules of ALA) are not neurotoxic *in vivo* when administered in large amounts to animals and humans. Concentration of these precursors in the brain or cerebrospinal fluid (CSF) of porphyric patients is substantially below that required for demonstrable toxicity *in vitro*. Litman and Correia, 1985, hypothesized that depletion of hepatic heme, as seen in AIP, leads to elevated tryptophan content and 5-hydroxytryptamine turnover in the brain, and is responsible for the neurological symptoms of AIP (17). On this basis then, administration of exogenous ALA would not lead to a depletion of hepatic heme and, therefore, would not be expected to elicit the neurological symptoms of AIP. Photosensitivity, associated with high systemic levels of Pp IX, is a typically finding in Erythropoietic Protoporphyrinemia (EPP) which is associated with decreased activity of ferrochelatase, the enzyme that converts Pp IX to heme. EPP is entirely cutaneous, with none of the hemolytic or neurological problems of other porphyrias.

Mild transient nausea and occasional vomiting have been observed following oral administration of high doses of ALA. Webber et al. 1997, observed that almost one-quarter of all patients who retained ALA had at least one abnormality in liver function tests (18). Nausea and vomiting were seen in 20% of the patients but no other symptoms of porphyria.

The most common complaint, due to Pp IX photosensitization, is very unpleasant pricking, itching or burning sensation under the skin after exposure to the sun. A systemic load above 10 mg/kg is required to develop skin photosensitization (DUSA Pharmaceuticals/Sun Pharma), which lasts from approximately 24 to 48 hours following ALA administration.

### **3.2 Invasive Brain Tumor**

The tumor may take on a variety of appearances, depending on the amount of hemorrhage, necrosis, or its age. An MRI will usually show a nonhomogeneous mass with a hypodense center and a variable ring of enhancement surrounded by edema. Mass effect from the tumor and edema may compress the ventricles and cause hydrocephalus. Cancer cells with stem cell-like properties have been found in glioblastoma (this may be a cause of their resistance to conventional treatments, and high re-occurrence rate (19).

The current treatment of patients with brain tumors is traditionally divided into surgical, radiotherapeutic, chemotherapeutic, and experimental treatments. Surgery is usually performed to either fully resect or debulk the gross portion of the tumor (contrast-enhancing portion). Although surgery alone rarely cures a malignant brain tumor, reduced tumor burden allows the body's own immune system or adjuvant therapies a greater chance of success. Biopsies are usually reserved for tumors in areas of the brain that are considered eloquent (harboring critical cerebral functions; i.e. language, motor, vision, functions, etc.) or when the patient's medical condition does not predict a safe surgical outcome. Radiotherapy plays a central role in the

management of brain tumors in individuals older than 4 years of age. Radiotherapy is generally regional, with a boost to the tumor bed, for a total of 6,000 cGy over 30 treatments in 6 weeks. Chemotherapy continues to be offered to brain tumor patients as adjuvant treatment. It is usually delivered intravenously but oral agents such as Temodar have shown some efficacy. Chemotherapy impregnated wafers (BCNU) are sometimes implanted at the time of surgery. Experimental protocols, including immunotherapy and gene therapy, round out the efforts attempting to better treat these deadly neoplasms.

The median survival of a patient undergoing biopsy of GBM without surgical resection or further treatment is ~8 weeks. For those patients who undergo surgery alone, the median survival increases to 17 weeks. The addition of radiation therapy post-surgical resection raises median survival to approximately 37 weeks; chemotherapy adds an additional few weeks to this median survival. Overall, the 5-year relative survival rate for a primary malignant glioma is age dependent. Survival rates are 63.1% for age 0-19, 50.4% for age 20-44, 14.2% for age 45-64, and 4.9% for age >65. Recurrence of the tumor at the site of surgical resection is the rule. The recurrence is within 2cm. of the margin of the resection cavity in 80% of cases. For patients with recurrent tumors undergoing repeat surgical resection, the re-operation may add as much as 14 to 30 weeks of additional survival. Nevertheless, this response is met with fatal growth in virtually all patients. The 5-year survival rate is less than 5%.

Lower grade tumors offer better prognosis. Median survival is 5.9 years when treated with biopsy alone. However, early resection of low grade tumors improves 5-year survival to 74% compared to 60% for biopsy and watchful waiting (19). As in malignant glioma, survival rates are age dependent. The ten-year survival rates are 86% for age 0-20, 53% for age 20 to 64, and 20% for age >64. Maximal tumor resection may improve both symptoms and survival rates (6, 20).

### **3.3 Rationale for ALA**

5-aminolevulinic acid (ALA) is a naturally occurring amino acid and a precursor in heme biosynthesis. ALA is produced at the cytosolic surface of the mitochondrial membrane and then transported to the cellular cytosol for heme biosynthesis. The availability of ALA in the cell cytoplasm is the rate-limiting factor in heme biosynthesis in all but erythropoetic cells. The heme biosynthetic enzymes are more active in glial tumors of the brain than in normal brain tissue. As a result, addition of ALA (the rate-limiting precursor) to malignant glial cells leads to an increase in the intracellular accumulation of Protoporphyrin IX, a fluorescent intermediary in heme biosynthesis. As a result, malignant glial cells fluoresce red relative to dark normal brain tissue, when viewed under ultraviolet light (300 nm). This effect enables more complete surgical removal of malignant glial tumor from within normal brain tissue.

### **3.4 Rationale for the Intraoperative Fluorescence/Reflectance Probe**

Although ALA results in visible concentrations of Pp IX in high grade malignant gliomas, detection in lower grade gliomas is limited due a relatively low intensity of fluorescence signals, resulting in incomplete tumor detection. However, Pp IX does accumulate to diagnostically significant levels in low grade gliomas even when not visibly evident to the

surgeon (21). To aid in the quantitative detection of subvisual concentrations of Pp IX in low grade gliomas, an intraoperative fluorescence/reflectance probe was custom designed under NIH funding. The intraoperative probe is a 1.25 mm semi-rigid, blunt end device that is placed in gentle contact with brain tissue by the surgeon for 3-5 seconds to make a spectroscopic measurement. The probe delivers a very small amount of blue light and white light to measure the concentration of Pp IX.

The probe meets all of the criteria necessary for classification as a non-significant risk device according to FDA guidelines. The device is non-invasive with respect to the participant and does not present a serious risk to the health, safety, or welfare of a subject. The device is not used to diagnose, cure, mitigate, or treat disease without concordance from additional data made available through practices which meet or exceed standard-of-care. The light exposure levels are below those known to cause any temperature rise or other significant tissue damaging effects, even in conjunction with ALA which can be phototoxic but at much higher light exposure thresholds.

## **4. PATIENT SELECTION**

### **4.1 Eligibility Criteria**

4.1.1 Patients entering into this study will have the presumptive diagnosis of high grade or low grade glioma based on imaging studies, or will have recurrent high-grade or low grade gliomas that have previously undergone diagnosis (astrocytoma, oligodendroglioma, mixed oligo-astrocytoma, anaplastic astrocytoma, and glioblastoma multiforme). Both of these groups will be undergoing craniotomy for tumor resection.

4.1.2 Patient age 18 to 72 years.

4.1.3 Karnofsky performance of 60% or greater, see Appendix B.

4.1.4 Patients must have normal organ and marrow function as defined below:

Leukocytes	>3,000/ $\mu$ L
Absolute neutrophil count	>1,500/ $\mu$ L
Platelets	>100,000/ $\mu$ L
Total bilirubin	within normal institutional limits
AST (SGOT)/ALT (SGPT)	<2.5 X institutional upper limit of normal
Creatinine	within normal institutional limits
	or
Creatinine clearance	$\geq 60$ mL/min/1.73 m  for patients with creatinine levels above institutional normal.

4.1.5 The effects of Aminolevulinic Acid (ALA) on the developing human fetus are unknown. Therefore, women of child-bearing potential and men must agree to use adequate contraception (hormonal or barrier method of birth control; abstinence) prior to study entry and for the duration of study participation.

- 4.16 Patient must have the ability to understand and the willingness to sign a written informed consent document or have a parent or guardian with the ability to understand and the willingness to sign the written informed consent.

## 4.2 Exclusion Criteria

- 4.2.1 History of allergic reactions attributed to compounds of similar chemical or biologic composition to aminolevulinic acid (ALA).
- 4.2.2 Personal or family history of Porphyrrias.
- 4.2.3 Uncontrolled intercurrent illness including, but not limited to ongoing or active infection, symptomatic congestive heart failure, unstable angina pectoris, cardiac arrhythmia, or psychiatric illness/social situations that would limit compliance with study requirements.
- 4.2.4 Pregnancy since aminolevulinic acid (ALA) is of unknown teratogenic or abortifacient effects.

## 4.3 Inclusion of Women and Minorities

Both men and women and members of all ethnic groups are eligible for this study.

## 4.4 Study Calendar

Baseline evaluations are conducted 3 weeks prior to start of protocol.

	Pre-Study	Day 1	Day 2-3	Day 14 (+/- 5days)
ALA a		X		
Informed consent	X			
Demographics	X			
Medical history	X			
Concurrent meds	X			X
Physical exam	X		X	X
Vital signs	X		X	X
Height	X			
Weight	X			X
Performance Status	X			X
CBC, w/diff, platelets	X		X	X
Serum chemistry b	X		X	X
EKG (as indicated)	X			
Adverse event evaluation	X		X	X

Confidential

MRI Brain + gadolinium	X		X c	
B-HCG	X d			

- a: ALA dose of 20 mg/kg oral administration one time.
- b: Albumin, alkaline phosphatase, total bilirubin, bicarbonate, BUN, calcium, chloride, creatinine, glucose, LDH, phosphorus, potassium, total protein, SGOT(AST), SGPT (ALT), sodium.
- c: MRI immediately post-operation (24-48 hrs post surgery).
- d: Serum pregnancy test (women of childbearing potential).

## 5 TREATMENT PLAN

The study will consist of 300 patients with high-grade or low-grade tumors that meet the eligibility criteria provided in section 4.1. Each patient will be evaluated and found to have a high-grade or low-grade glioma by means of history and recent imaging studies (MRI) and deemed a surgical candidate based on current neurosurgical standards of care. The study will have the University of California San Francisco (UCSF) ethics committee (CHR) approval. Informed consent will be obtained from patients meeting enrollment criteria. The study will be done according to the guidelines of the International Conference on Harmonization - Good Clinical Practice.

### 5.1 Pre-surgical Procedure

A one-time single administration of aminolevulinic acid (ALA), at a dose of 20 mg/kg body weight, will be given orally. ALA will be dissolved in ~100 mL of drinking water or juice and given to the patient approximately 3 hours before anesthesia.

### 5.2 Surgical Procedure

ALA will be mixed in the minimum volume of sterile water or juice immediately before use and given as a single bolus orally approximately 3 hours prior to scheduled anesthesia. Image-guided microsurgical resection of the tumor will be undertaken. Following the standard tumor resection under light microscopy, the residual tumor bed will be illuminated with blue light via a high pass optical filter in the microscopes light chain. The surgeon will examine the tumor bed with a barrier filter in the optical chain of the surgical microscope. The surgeon will quantitatively measure the concentration of Pp IX by placing the intraoperative fluorescence/reflectance probe in gentle contact with brain tissue by the surgeon for 3-5 seconds to make a recording. If fluorescence is present, and if safe, small biopsies will be taken from those areas of fluorescence as well as from non-fluorescing regions in the tumor resection cavity. When possible, the intent would be to collect a number of biopsies with a range of fluorescence intensities from each patient (at least one biopsy from normal-appearing tissues and at least one from the most fluorescent area). All biopsy specimens, including those taken from the bulk tumor, will be reviewed by a neuropathologist to assess tumor content. The expectation is that residual fluorescent tissue in the tumor cavity will be surgically removed (if deemed safe by the

neurosurgeon), potentially leading to more complete tumor resection. Pathologic confirmation of tumor type will be made by neuropathology.

Biopsies of fluorescent and non-fluorescent tissue within the tumor cavity will be graded by the surgeon at the time of biopsy as 0 to 3 fluorescence. A screen shot of the fluorescent image of the resected tumor illuminated with blue light via a high-pass filter will be documented for each patient with an integrating video camera. The fluorescence intensity and the quantitative measurement obtained with the intraoperative probe corresponding to each area on the screen shot from which biopsy is taken will be recorded by the surgeon in the operating room. The sample will be snap frozen in the operating room and provided to the pathologist for grading the tumor from 0 to 3 based on the degree of cellular infiltration. The scale to be used for grading is as follows:

Grade	Surgeon (intensity of fluorescence)	Pathologist (cell density)
0	No fluorescence	No tumor cell density content
1	Mild brightness	Mildly infiltrating tumor cell density
2	Moderate brightness	Moderately infiltrating cell density
3	Intense brightness	Highly infiltrating cell density

The surgeon is responsible for:

- Identifying at least one fluorescent area within the tumor cavity and performing biopsy and grading that site's fluorescence.
- Identifying at least one non-fluorescent area within the tumor cavity and performing biopsy and grading that site's fluorescence.
- Labeling the areas (i.e. fluorescent or non-fluorescent) from which the biopsies are taken.

The pathologist is responsible for:

- Grading each frozen section biopsy for tumor content on a scale of 0 to 3.
- Labeling of specimens to be certain they correlate with biopsies taken by the surgeon.

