## **7 STATISTICAL CONSIDERATIONS**

### **7.1 Study Endpoints**

This is a single-center, single arm, open label phase II trial of fluorescence-guided resection by use of 5-aminolevulinic (ALA) at a dose of 20 mg/kg body weight in glioma patients. We hypothesize that surgical removal of the residual fluorescent tissues in the tumor cavity, presumably representing tumorous cells, will result in an increase in the amount of tumor removal during neurosurgical resection. In addition, we hypothesize that for recurrent malignant glioma, that the fluorescent material will reflect active viable tumor and not changes related to treatment such as macrophages or gliosis.

The primary analysis will be based on one biopsy taken from the most fluorescent area and one from normal appearing tissues for each patient as judged by the neurosurgeon.

The endpoints of interest in this study are as follows:

- Primary Endpoint: Positive Predictive Value (PPV), defined as the percentage of biopsies taken from the most fluorescent tissues determined by the pathologist as having tumorous content.
- Second Endpoints:
  - Negative Predictive Value (NPV), defined as the percentage of biopsies taken from non-fluorescent tissues determined as having no tumor content by the pathologist.
  - The safety of the use of 5-aminolevulinic (ALA) at a dose of 20 mg/kg body weight for neurosurgical resection in glioma patients
  - The correlation between fluorescent intensity as scored by the neurosurgeon and the tumor content as scored by the pathologist
  - The percentage of patients for whom there is no fluorescent tissue after surgery

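### Section 5.2 puts the surgeon's probe reading before biopsy and the 0-3 visual score, with neither site choice nor score fixed first, so both may be influenced by the probe, mainly in the low-grade subgroups

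*Combined protocol and SAP*

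**What the plan says.** Section 5.2 describes the intraoperative steps in this order:

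- Visual inspection: "The surgeon will examine the tumor bed with a barrier filter in the optical chain of the surgical microscope".
- Probe reading: "The surgeon will quantitatively measure the concentration of Pp IX by placing the intraoperative fluorescence/reflectance probe in gentle contact with brain tissue".
- Biopsy: "If fluorescence is present, and if safe, small biopsies will be taken from those areas of fluorescence as well as from non-fluorescing regions".

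The probe and biopsy sentences adjoin, with no step between them: "to make a recording. If fluorescence is present, and if safe, small biopsies will be taken".

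On the score, the same section says that biopsies "will be graded by the surgeon at the time of biopsy as 0 to 3 fluorescence". The surgeon also records, for every biopsied site, "The fluorescence intensity and the quantitative measurement obtained with the intraoperative probe corresponding to each area on the screen shot from which biopsy is taken". The list of responsibilities in 5.2 gives the surgeon the identification, labeling and grading of sites. The grading table anchors the surgeon's scale to visible brightness.

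Section 3.4 explains why the probe is there: "Pp IX does accumulate to diagnostically significant levels in low grade gliomas even when not visibly evident" to the surgeon.

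Section 7.1 bases the primary analysis on "one biopsy taken from the most fluorescent area and one from normal appearing tissues for each patient as judged by the neurosurgeon". PPV uses the most fluorescent biopsy, NPV uses biopsies of non-fluorescent tissue, and a further secondary endpoint correlates the surgeon's intensity score with the pathologist's score. Section 7 does not mention the probe.

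**The concern.** The PPV, NPV and correlation endpoints all depend on what one surgeon judges to be fluorescent. If that surgeon already knows the probe value when choosing and scoring a site, the judgement may no longer rest on sight alone. In a low-grade tumor with little or no visible glow, a raised reading could lead the surgeon to pick that site as the most fluorescent one or to score it 1 rather than 0. A dark site with a raised reading could equally be passed over as the non-fluorescent sample.

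The results would then be reported as fluorescence seen and scored by the surgeon, although a custom-built probe had helped to produce them. The records would not show which practice was followed, and the order of events cannot be reconstructed after surgery.

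**Working it through.** The point is procedural, so the main check is to set the passages side by side.

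1. **Order.** The probe sentence in 5.2 follows the visual inspection and precedes the biopsy sentence. No site selection, label or score is recorded at the inspection step. Scoring comes at biopsy, so on the written order it follows the probe reading.
2. **Observer.** The surgeon places the probe, chooses and labels the sites, gives the score, and records both the intensity and the probe value. No passage withholds the reading or locks the visual choice first.
3. **Meaning of fluorescence.** The condition that triggers biopsy comes directly after the probe sentence and does not say whether visible or probe-detected fluorescence is meant. The grading table points to visible brightness. Section 7.1 does not settle it.
4. **Where eye and probe would differ.** Section 3.4 says that ALA gives visible Pp IX in high-grade glioma and places the subvisual problem in lower grades. That is two of the six subgroups in 7.2: 2 x 50 = 100 of 6 x 50 = 300 patients.

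**The plan's own figure.** Section 7.2 gives n = 50 per subgroup, null PPV 80%, target PPV 92%, one-sided alpha 0.10, about 90% power, and success at 44 or more. With X ~ Binomial(50, p):

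- P(X >= 44 | p = 0.92) = 0.898, which reproduces the stated power.
- P(X >= 44 | p = 0.80) = 0.103, close to the stated 0.10.

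**How sensitive the rule is to steering.** The inputs in this step are assumptions, not figures from the documents, and they do not estimate bias. Suppose a fraction f of the most fluorescent sites is moved by the probe from sites with PPV a to sites with PPV b. Then p = a(1 - f) + bf.

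| a (by eye) | b (moved sites) | f | p | P(X >= 44) |
|---|---|---|---|---|
| 0.80 | 0.92 | 0 | 0.800 | 0.103 |
| 0.80 | 0.92 | 0.10 | 0.812 | 0.145 |
| 0.80 | 0.92 | 0.25 | 0.830 | 0.231 |
| 0.80 | 0.95 | 0.10 | 0.815 | 0.158 |
| 0.80 | 0.95 | 0.25 | 0.8375 | 0.276 |
| 0.92 | 0.80 | 0 | 0.920 | 0.898 |
| 0.92 | 0.80 | 0.10 | 0.908 | 0.827 |
| 0.92 | 0.80 | 0.25 | 0.890 | 0.691 |

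For example, 0.80 x 0.75 + 0.92 x 0.25 = 0.83. If moved sites carry tumor more often than those chosen by eye, the chance of success rises. If they carry it less often, it falls. The documents give neither f nor b, so they fix neither size nor direction.

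**The case against.** A reader might infer from the sentence order that PPV, NPV and the correlation are contaminated by the probe. The documents do not support that.

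- The order comes from the sequence of sentences, not from a stated rule, and a visual inspection precedes the probe.
- The text that ties a probe value to each biopsied area fits equally well with probing sites already picked by eye.
- No passage says that the reading guides site choice or changes the score.
- The scale is anchored to brightness, so a site with no glow and a raised reading is properly a 0. Section 7.1 also uses a visual term for the comparison biopsy.
- A blue-light screen shot is kept for each patient and gives some independent check on the labels.
- High-grade tumors are expected to fluoresce visibly, so the mechanism has much less room in the other four subgroups.

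All of this stands, and it limits the point to a risk. It does not remove it. The text allows both practices, and even when sites are picked by eye the score may still be given after the reading is known. The screen shot documents appearance, but the plan assigns no one to check scores against it.

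A reader might also infer that an eye-versus-probe comparison is lost. No such comparison is among the endpoints or analyses in Section 7, so that is not a harm to this plan.

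**Conclusion.** The point holds as an open route for bias, not as a demonstrated bias. On the written order of 5.2, the surgeon has the probe value before biopsying and scoring, and nothing fixes site choice or score beforehand. The most fluorescent and non-fluorescent selections and the surgeon's score may be influenced as a result, chiefly in the two low-grade subgroups.

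This rests on two assumptions: that the sentences in 5.2 reflect the order followed in the operating room, and that the surgeon sees the reading as it is taken. Neither is stated outright. The table of assumed steering shows only that the 44-of-50 rule responds to modest shifts in PPV either way. It should not be read as a claim that the reported PPV will be too high. The change is worth making because it is cheap and the sequence cannot be recovered afterwards.

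**What to change.** In 5.2, have the surgeon select, label and score (0-3) the sites by eye under blue light, and have these entries recorded before the probe is placed on those sites. This moves the grading from the time of biopsy to just before probing. Because the score is already on record, the reading need not be hidden from the surgeon.

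In 7.1, state that fluorescent and non-fluorescent for PPV and NPV mean visual score 1-3 and 0. State also that any site added because of a probe reading is flagged and kept out of the primary pair of biopsies.

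The sample size of 50 per subgroup and the 44-of-50 rule are unchanged, and no extra biopsy or device is needed. The cost is slightly more operating time and possibly fewer sites counted as fluorescent in the low-grade subgroups.
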